9.2. Statistical methods

Basic baseline statistics including means (SDs) and frequency distributions (percentages) will be reported for demographic characteristics, subjective and objective measures (such as smoking history, the number of cigarettes and other nicotine products, and smoking topography measures). Where necessary, some characteristics will be reported by the two groups under investigation. Numerical baseline characteristics will be compared between the two groups using two-sample T-test or nonparametric Wilcoxon Rank-Sum test when appropriate. Suitably transformed variables will be used when necessary. Categorical variables will be compared using chi-square tests or Fisher's exact tests. Separate baseline analysis will be done within black and white samples in this study.

To determine the effect of progressive nicotine content reduction (NCR) on cotinine and other biomarkers of smoking exposure in both black and white smokers of lower SES over the 18 week trial period: for each of the biomarkers and other outcome variables of interest, exploratory data analysis will be conducted within each time period and across. Results will be summarized by table and figures (such as boxplots). Profile plots will be generated to show the trajectory of variable across different time periods. The major analytical tool for addressing the specific aims of this study is linear mixed models with repeated measures. For each biomarker and other numerical outcome measures of interest, a linear mixed model for repeated measures will be fit to evaluate the main effects of time, group, and time-by-group interaction; treating baseline scores for outcomes as covariates. Known confounders will be included in the linear models, and other covariates will be included if their individual bivariate associations with both the group variable and outcome are significant at 10% level. The magnitude and direction of the difference between the treatment groups will be quantified by reporting the estimated least-square mean differences at each time point. Separate analysis will be performed in black and white samples individually. We will also test for a number of potential effect modifiers by pooling the trial data of white smokers and black smokers together. Interaction terms that do not reach statistical significance will be dropped from the final model.

To determine the modifying effect of menthol on progressive nicotine content reduction and biomarkers: modification effects such as the menthol will be examined by incorporating the menthol-by-group interaction in the multi-variable linear mixed model. The three-way interaction of the menthol-by-group-by-time will be explored but will be removed from the model if not significant. If the menthol-by-group interaction were found significant then mean-profile plot will be used to show the interaction in details.

To determine the predictors of participant drop-out/relapse: it is hypothesized that compensatory smoking behavior as measured by smoking topography and expired carbon monoxide, a higher baseline nicotine dependence behavioral score and rapid nicotine metabolism phenotypes will be associated with drop-out/relapse. The status of drop-out/relapse will be combined with the length of time from randomization to drop-out/relapse or loss of follow-up to form a time-to-event type of variable. Participants who completed the randomization phase of study will be considered as censored records. Kaplan-Meier type analysis (for categorical predictors) or simple Cox proportional hazard regression model (for quantitative predictors) will be used to examine the bivariate associations between the possible predictors and time to drop-out. If a predictor has shown marginal significance (with p-value less than 0.10) in the bivariate analysis then it will be kept in the multiple regression analysis. A multi-variable Cox proportional hazard regression

model will be built to examine the effects of the predictors jointly for time to drop-out. The magnitude and direction of effectiveness will be quantified by the estimated hazard ratios with their 95% confidence intervals. The interaction between the predictors will be explored in the analysis but will be removed if not significant.

To determine if a gradual reduction in reduced nicotine content cigarettes vs. same nicotine content is associated with a reduction in stress: the stress level is measured by both salivary biomarkers and psychological variable. Cortisol values measured at different time of a day will be summarized to peak daily cortisol and cortisol drop variables. Summary statistics will be generated to describe the trend of cortisol variables over visit by group. T-tests or nonparametric Wilcoxon Rank-sum test will be used to compare salivary cortisol measures between the two study groups at each time point. Similar to previously described, linear mixed model for repeated measures will be fit to evaluate the main effects of time, group, and time-by-group interaction; treating baseline cortisol scores as a covariate. The psychological variables for stress levels will be analyzed in a similar statistical fashion.

10. Confidentiality, Privacy and Data Management

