7.4.3. Method for Assigning Subject to Treatment Groups

Participants will be randomized to one of two experimental conditions based on a pre-determined random number sequence generated by Biostatistics core. Randomization will be stratified by site (Penn State and George Washington University) and by menthol flavor (regular/menthol). This ensures a similar distribution of treatment assignment (1:1 for gradual reduction: control) across study sites to avoid potential confounding.

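### Section 9.2 screens covariates by a test against randomised group and leaves the rest unlisted; a list fixed in advance, with the strata in it, is a small and free improvement

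*Combined protocol and SAP*

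**What the plan says.** Section 9.2 describes one linear mixed model per biomarker, with time, group and their interaction, "treating baseline scores for outcomes as covariates". Covariates can then enter by two routes. The first is untested: "Known confounders will be included in the linear models", with none named. The second is a double screen: "other covariates will be included if their individual bivariate associations with both the group variable and outcome are significant at 10% level". No candidate list is given, and the text does not confine the candidates to variables measured before randomisation. The models are also fitted by race: "Separate analysis will be performed in black and white samples individually". Interactions that are not significant are dropped, with no exception stated for time-by-group.

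Section 7.4.3 stratifies randomisation by site and by menthol flavour and gives the reason: "This ensures a similar distribution of treatment assignment (1:1 for gradual reduction: control) across study sites to avoid potential confounding". In Section 9.2, site is named in no model. Menthol is named for Aim 1b, where the effect is examined by "incorporating the menthol-by-group interaction in the multi-variable linear mixed model", but not in the Aim 1a paragraph.

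**The concern.** Randomisation makes treatment group independent of every baseline variable, so a test of a baseline covariate against group can detect only chance imbalance. It says nothing about whether the covariate predicts cotinine, which is the reason to adjust for it. A strong predictor that happens to be balanced is excluded, and the same predictor is included if the arms happen to differ.

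Three things follow:

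- The Aim 1a model cannot be written down until the arms have been compared.
- The screen is repeated for each biomarker and each race, so the black and white cotinine results may be adjusted for different variables.
- Blocked, stratified randomisation suppresses imbalance in site and menthol flavour. If these two are not among the unnamed confounders, the screen tends to exclude exactly the variables that the design singled out.

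The screen for drop-out predictors, also in Section 9.2, uses association with the outcome alone. The group criterion is thus specific to the treatment-effect models, where randomisation makes it uninformative.

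**Working it through.** **1. The plan's own figure.** Section 9.1 gives SDs of 120 and 116, 70 per group and alpha 0.05 (two-sided assumed). The pooled SD is √((120² + 116²)/2) = 118.0. The standard error is 118.0 × √(2/70) = 19.9, and 58/19.9 = 2.91. Power is Φ(2.91 − 1.96) = 0.83; with SD 120 it is 0.82. At 68 ng/ml it is 0.92 to 0.93. Both stated claims hold, and 280/0.70 = 400.

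**2. How the screen behaves.** Two simulations kept the baseline outcome in every model, as Section 9.2 does, with 70 per arm and SD 118. Assumed inputs, absent from the documents: correlation of baseline with outcome 0.5 or 0.7, and one further baseline covariate explaining a share R² of the residual variance. One simulation was a single-visit ANCOVA (8,000 replicates per cell). The other used the six post-randomisation visits, Visits 4 to 9, with unstructured covariance, complete data and the effect rising to 58 ng/ml at Visit 9 (2,500 replicates per cell). Ranges cover both.

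| R² | Covariate enters | Model SE, rule ÷ fixed | True SD of estimate, rule ÷ fixed |
|---|---|---|---|
| 5% | 6–9% | 1.020–1.021 | 1.011–1.016 |
| 10% | 8–11% | 1.044–1.047 | 1.025–1.038 |
| 20% | 9–11% | 1.103–1.105 | 1.051–1.079 |

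In the single-visit simulation a non-prognostic covariate entered in about 1% of trials.

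A hand check on the SE column: leaving the covariate out inflates the SE by 1/√(1 − R²), which is 1.026, 1.054 and 1.118. Weighting by the share of trials that omit it gives 1 + 0.93 × 0.026 = 1.024, 1 + 0.91 × 0.054 = 1.049 and 1 + 0.90 × 0.118 = 1.106. The simulated ratios are slightly lower because fixed adjustment pays a little for the extra coefficient.

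The model SE grows more than the true SD, so inference is slightly conservative. Type I error was 4.0–5.3% under the rule and 4.4–5.4% with fixed adjustment. The Monte Carlo standard error at 2,500 replicates is √(0.05 × 0.95/2500) = 0.4 points.

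**3. Power at 58 ng/ml, rule / fixed.**

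| Baseline correlation | R² | Single visit | Repeated measures |
|---|---|---|---|
| 0.5 | 5% | 0.911 / 0.919 | 0.918 / 0.926 |
| 0.5 | 10% | 0.917 / 0.940 | 0.918 / 0.935 |
| 0.5 | 20% | 0.925 / 0.961 | 0.904 / 0.952 |
| 0.7 | 5% | 0.980 / 0.982 | 0.981 / 0.982 |
| 0.7 | 10% | 0.984 / 0.989 | 0.978 / 0.985 |
| 0.7 | 20% | 0.983 / 0.994 | 0.976 / 0.990 |

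The smallest loss is 0.982 − 0.981 = 0.1 points and the largest 0.952 − 0.904 = 4.8 points. The lowest power under the rule is 90%.

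**4. Black and white models.** If a covariate enters each race's model independently with probability q, the two models differ on it with probability 2q(1 − q). For q = 0.059 this is 2 × 0.059 × 0.941 = 0.11; for q = 0.109 it is 2 × 0.109 × 0.891 = 0.19.

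**5. The strata.** Further assumptions: permuted blocks of 2 to 20, menthol use of 80% and 35% by race, random 30% drop-out, and site and menthol each explaining 2.5%, 5% or 10% of outcome variance. Under the double screen, site enters 1.7–5.1% and menthol 2.4–7.1% of single-race analyses, and each enters 0.2–0.5% of pooled analyses. Without blocks, entry is 4.2–9.5% within a race and 7.4–10.3% pooled. Omitting both strata adds 0.4% to 3.3% to the standard error when together they explain 5% to 20%.

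**The case against.** The strongest reply is that little is at stake. The baseline outcome is always in the model and removes the largest share of explainable variance. A further covariate explaining 10% or 20% of what remains is an optimistic assumption, and at 5% the power loss is under one point. Section 1.3.2 also lists the biomarkers as secondary endpoints, although Section 9.1 sizes the trial on cotinine. This stands, and it is why the point is rated low.

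Second, the strata may already be covered. Section 7.4.3 speaks of site in terms of confounding, and the Aim 1b model could be read as the same model with menthol added. This also stands. A reader might infer that the plan omits its stratification factors from the analysis; the text supports only that Aim 1a does not name them.

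Third, different black and white models have no shown consequence for validity. With baseline covariates, each within-race estimate remains unbiased whichever of them enter, and effect modification is tested in pooled data. A reader might infer that the race comparison is biased; the documents do not support that. What remains is a loss of comparability in how the two results were adjusted.

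A reader might also infer a large loss of power. A model with one covariate correlated 0.5 with outcome and no baseline outcome gives 84% under the rule against 91% with fixed adjustment. That is not the planned model, so those figures do not apply.

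**Conclusion.** The point holds as a low-severity, free improvement. For baseline covariates the group test selects on chance imbalance, leaves a prognostic covariate out about 90% of the time, and means that the Aim 1a covariate set is not fixed in advance. Under the assumed R² values the cost is a model standard error about 2%, 5% or 10% larger and 0.1 to 4.8 points of power, with power still above the stated 80%. The black and white models would differ on a given prognostic covariate in about 11–19% of trials.

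The tempting stronger reading is that data-driven selection biases the treatment effect or inflates type I error. For baseline covariates, with the rule followed as written, the calculations show neither. That conclusion has a limit: Section 9.2 does not confine its other covariates to baseline. Screening variables measured after randomisation, which treatment may have changed, could introduce bias. If the screen were run on completers only, differential drop-out could also drive the group test.

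All sizes depend on the assumed R², correlations, block sizes and menthol shares. The direction does not.

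**What to change.** Replace the sentence on known confounders and the 10% screen with text such as:

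> Each linear mixed model will include time, group, time-by-group, the baseline value of the outcome, site and menthol flavour, plus race in pooled models, and any further baseline prognostic covariates listed here before unblinding. Only variables measured before randomisation will be used, the same list will apply to the black and white analyses, and no covariate will be added or removed on the basis of a test against treatment group.

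State also that the rule for dropping non-significant interactions applies only to exploratory effect-modifier terms and never to time-by-group. Without this the final model would still depend on the data.

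Section 21.7 has the Biostatistics Core prepare unblinded reports during the trial, so the covariate list should be dated and drawn up without reference to them.

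The cost is SAP wording and a few degrees of freedom. Site, menthol flavour and baseline values are already collected, and the sample size does not change. If site and menthol flavour were always meant as known confounders, the new text simply says so.

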Stress is the major reason why youths and adults smoke. Cigarette smokers report that cigarettes help them calm down and relax. However the relationship between stress and smoking is still not well understood. Nicotine increases physiological stress through activation of the hypothalamic-pituitary-adrenal (HPA) axis, producing the stress hormone cortisol. Studies indicate that smokers have higher salivary levels of cortisol throughout the day than nonsmokers (Figure 1, data from: Steptoe A et al. [31]). Cortisol is also elevated in adults with lower SES compared to higher SES adults, although the findings are not consistent [32]. Although smokers report immediately after smoking that they have reduced stress, the response is acute and may reflect a temporary relaxed state while taking a break. Studies show that within half an hour after smoking, reported psychological stress levels in smokers return to their normal high levels [33]. This is supported by data showing that quitters have reduced psychological stress levels compared to persons who continue to smoke [34]. In the current study, we suggest that an important endpoint in a reduced nicotine policy for all smokers, but particularly for low SES

smokers, is that physiological and psychological stress should not be increased but decreased in a reduced nicotine regimen. An assessment of whether the gradual reduction in nicotine content of cigarettes is associated with a reduction in stress is the major focus of Specific Aim 3 of this proposal.

In studying how different cigarettes affect nicotine dependence, cotinine is the most commonly used biomarker of nicotine uptake and exposure. It is easily measured by ELISA and discriminates with a high degree of precision exposure to mainstream smoke vs. environmental tobacco smoke. It is also used as a general marker of the dose of exposure. However, cotinine represents <15% of total urinary nicotine metabolites. Because the rate of nicotine metabolism varies among individuals and is associated with the degree of nicotine dependence, the genotypic and phenotypic variation of nicotine metabolism will likely be an important factor in determining in which smokers a nicotine reduction strategy might be successful. Examining metabolic phenotypes as predictors of participant drop-out/relapse will be the major focus of Specific Aim 2 of this proposal.

3. Inclusion and Exclusion Criteria

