9.1. Sample size determination

The primary sample size calculation for this project will be based on hypothesis 1a and the main outcome variable is plasma cotinine concentration (measured as ng/ml). The mean value of this continuous variable will be compared between the control group and the experimental group. For plausible effect size and variation, we use results of Benowitz et al [4], where the mean (SD) of plasma cotinine concentration are 240 (120) for the control group and 113 (116) for the experimental group at the 21st week follow-up visit (end of randomization phase for trial). It is expected that the cotinine level in the experimental group is reduced gradually after the randomization and the mean difference of the cotinine level between these two groups at the beginning of the trial for our study will be smaller than the value of 127 ng/ml in Benowitz et al [4]. With a sample size of 70 participants per group, we are able to detect the difference in plasma cotinine concentration level between the two groups as small as 58 ng/ml with at least 80% power (and 68 ng/ml with at least 90% power). In this project we plan to study the mean change of plasma cotinine concentration separately for black and white populations. A total sample size of 280 (70 per group * 2 groups * 2 races) is then needed for this project. We plan to recruit a total of 400 participants for this project by allowing a 30% drop-out rate. The alpha level used for the power analysis is 0.05. Another biomarker of interest is the Glutathione (GSH, measured in μ mol/ml). Within each study population (black or white), a sample size of 70 per

group will enable us to detect a mean difference of GSH of 0.23 with at least 90% power. The common standard deviation is assumed to be 0.40 based on [name] et al (2004). For testing the menthol-by-group interaction effects, our proposed sample size will give us at least 80% power to detect a mean difference of plasma cotinine concentration of 72 ng/ml in the pair-wise comparison of among the group-by-menthol combination (4 levels, alpha is adjusted to 0.0083 by Bonferroni method).

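### Section 9.2 tests an unlisted set of treatment-effect modifiers with no stated level, adjustment or exploratory label, and its drop rule lets chance interactions stay in the final model

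*Combined protocol and SAP*

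**What the plan says.** Section 9.2 of the combined protocol and SAP fits a linear mixed model for each biomarker and other numerical outcome. The arm effect is reported as least-square mean differences at each time point, and black and white participants are also analysed separately. Two sentences then follow: "We will also test for a number of potential effect modifiers by pooling the trial data of white smokers and black smokers together" and "Interaction terms that do not reach statistical significance will be dropped from the final model". No modifiers are named here, and no count, test level or reporting rule is given.

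Menthol has its own paragraph, which opens: "modification effects such as the menthol will be examined by incorporating the menthol-by-group interaction in the multi-variable linear mixed model". It is also the subject of Aim 1b (section 1.1). In section 9.1 it has its own power statement, "at least 80% power to detect a mean difference of plasma cotinine concentration of 72 ng/ml in the pair-wise comparison", for which "alpha is adjusted to 0.0083 by Bonferroni method". That is the only multiplicity adjustment in the documents. The general level is given only for sample size: "The alpha level used for the power analysis is 0.05".

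The word exploratory in 9.2 is attached to descriptive summaries and plots. The menthol-by-group-by-time term and the interactions among Cox predictors are to be explored. Neither phrase covers the pooled modifier tests.

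**The concern.** The drop rule lets significance decide which interactions the final model contains. Two things follow.

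First, the more modifiers are tried, the likelier it is that one survives by chance. Because the dropped ones need not be reported, a reader could not tell how many tests stand behind a surviving one.

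Second, once a group-by-modifier term is in the model, the arm coefficient refers to one level of the modifier, and a least-square mean difference is either level-specific or averaged over levels. The plan does not say that the reported differences come from a model without these terms, so the estimand can depend on which interactions happened to reach significance.

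This matters here because the study rationale (section 2.3) is about a nicotine policy for a varied population of smokers. A false modifier would read as a group in which reduction works less well.

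**Working it through.** **The plan's own figures.** Four group-by-menthol cells give 6 pairs, and 0.05/6 = 0.0083, as stated. The planning values are "the mean (SD) of plasma cotinine concentration are 240 (120) for the control group and 113 (116) for the experimental group". With SD 120 and 70 per cell (280/4, assuming an even menthol split), the standard error of a pairwise difference is 120 × √(2/70) = 20.28 ng/ml, and 72/20.28 = 3.55. The two-sided critical value at 0.0083 is 2.64, so power is Φ(3.55 − 2.64) = Φ(0.91) ≈ 0.82 (0.81 from the noncentral t). This agrees with the stated minimum of 80%. Menthol therefore has a coherent, adjusted power statement; no other modifier has one.

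**Chance of at least one false modifier, for one outcome.** Assumptions: k modifiers, none real, each tested at two-sided 0.05. Neither k nor the level is in the documents. With independent tests the chance is 1 − 0.95^k. The last column is a simulation with test statistics correlated at 0.5.

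| k | independent | correlation 0.5 |
|---|---|---|
| 2 | 9.8% | 9% |
| 5 | 22.6% | 18% |
| 10 | 40.1% | 29% |

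The search is repeated for each outcome. Five modifiers on five outcomes would give 1 − 0.95^25 = 72% if all 25 tests were independent. Correlated biomarkers would bring this down.

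**How large a surviving chance interaction would look.** Take SD 118.0 (root mean square of 120 and 116), a two-level modifier split evenly, and 70 per cell. The standard error of the difference between the two arm effects is 118.0 × √(4/70) = 28.2 ng/ml. Reaching p<0.05 needs an observed difference of 1.96 × 28.2 ≈ 55 ng/ml, which moves each level's arm effect about 28 ng/ml from the average. For scale, section 9.1 gives 58 ng/ml as the arm difference detectable with 80% power. This treats a single visit without baseline adjustment; adjustment would lower the threshold.

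**What retention does to the arm effect.** Simulation of one pooled endpoint: 280 participants, no true effects, k independent binary modifiers, each interaction tested at 0.05, significant ones kept, model refitted.

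| quantity | result |
|---|---|
| mean of the equal-weighted average arm effect | about 0 (no bias) |
| type I error of that average, 50/50 modifiers, k=5 and 10 | about 5% |
| same, 30/70 modifiers, k=5 | about 7% |
| same, 30/70 modifiers, k=10 | about 9% |
| type I error of the reference-level arm coefficient, k=5 to 10 | 9% to 17% |
| type I error with no modifier interactions in the model | about 5% |

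**The case against.** Several stronger readings are tempting, and the documents do not support them.

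- **That nothing distinguishes these tests from the menthol question.** Menthol has its own aim with a stated expectation, its own power statement with an adjusted alpha, and its own paragraph. What is missing is any status for the others.
- **That each modifier is tested at full alpha.** No level is given for these tests. The 0.05 is stated for the power analysis and is only inferred here.
- **That chance interactions necessarily enter the reported treatment result.** The least-square mean differences and race-specific analyses are described before the pooled tests, and the sample size is built by race. On one natural reading, the pooled tests are an addition that leaves the race-specific arm differences untouched. The text does not say which model supplies the reported differences, so the supportable word is *can*.
- **That the main comparison is biased.** The simulation shows no bias in the equal-weighted average, and no inflation with 50/50 modifiers.
- **That the background promises modifiers will show who benefits.** The clause "will likely be an important factor in determining in which smokers a nicotine reduction strategy might be successful" in section 2.3 is about variation in nicotine metabolism. The next sentence there assigns metabolic phenotypes to Aim 2, as predictors of drop-out or relapse, which is a separate Cox analysis.

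It is also fair to say that k could be small, and that menthol or race may be among the unlisted modifiers. All of this limits the size and certainty of the harm. It does not supply the missing list, level or label, nor remove the rule that significance decides which interactions are kept.

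**Conclusion.** The point stands in a limited form. Section 9.2 plans an open set of modifier tests for each outcome and keeps interactions by significance; that retention is the converse of the drop rule rather than an explicit sentence. The risk of a false modifier per outcome is about 10%, 23% and 40% for 2, 5 and 10 independent tests. Even two tests nearly double 0.05, so the conclusion does not depend on a large k. The effect on the arm comparison is smaller and conditional: none on the average with balanced modifiers, type I error of about 7% to 9% with 30/70 modifiers, and 9% to 17% for a reference-level coefficient. These figures rest on an assumed k, an inferred two-sided 0.05, independent binary modifiers, and the arm effect being read from the model after selection. This is a defect in a stated rule that is cheap to replace; it does not show that the Aim 1a comparison is invalid.

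**What to change.** In section 9.2, replace retention by significance with wording such as: *the treatment effect is reported from the model without these effect-modifier interactions; the time-by-group term stays*. The last clause is needed because the drop rule as written is not limited to modifiers.

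Add that:
- menthol-by-group (Aim 1b) and the planned race comparison keep their pre-stated status;
- all other group-by-modifier tests are exploratory and are fitted one at a time;
- the interaction estimate and 95% CI are reported for every modifier tested, significant or not.

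The cost is a change of wording and a longer supplementary table. No modifier beyond those with pre-stated status could be claimed as confirmed by this trial. Sample size, visits and data collection are unaffected.
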